## Synopsis

Title	Regorafenib in Adults $\geq$ 65 Years with Metastatic Colorectal Cancer: A Phase II Study
Clinical study phase	Phase II
Primary study objective	To assess grade 3-5 toxicity rates of regorafenib in older adults with implementation of focused education and support initiatives
Indication	Refractory metastatic colorectal cancer (mCRC)
Diagnosis and main criteria for inclusion	
 
1. Histologically or cytologically confirmed colorectal carcinoma
 
2. Evidence of measurable (by RECIST criteria) metastatic disease
 
3. Age 65 years or over
 
4. Progression of disease on previous therapy, deemed not a candidate for further standard therapy by treating oncologist, or patient declines other options
 
5. ECOG PS 0-1
 

Study design	Single-arm, open label Phase II study
Type of control	Historical
Number of subjects	60
Plan for statistical analysis	
Adverse events will be grouped by system organ class and graded using NCI CTCAE version 4.0. Descriptive statistics for grade 3/4 toxicity rates and all-grade skin (HFS) toxicity will be assessed. Relative dose intensity for regorafenib will be calculated.
 
Based on expected grade 3-4 toxicity rates of 40-50%, a sample size of 60 patients will give approximately 10% margin of error with 95% confidence interval.
 
Secondary outcomes for efficacy will be response rate (RR), progression-free survival (PFS) and overall survival (OS). Kaplan-Meier curves will be used to estimate median PFS and OS.

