## 12. Statistical Methods and Determination of Sample Size

### Statistical and analytical plans

The primary end-point is grade 3-5 toxicity incidence rates. Adverse events will be grouped by system organ class and graded using NCI CTCAE version 4.0. Descriptive statistics (counts and percentages) for grade 3 and 4 toxicity rates and all-grade skin toxicity will be assessed and evaluated in relation to CGA domains.

Relative dose intensity (dose reductions, dose delays, or inability to tolerate treatment) for regorafenib will be calculated. Specific toxicities associated with dose reductions, delays and/or early discontinuation of treatment course will be identified.

Efficacy outcomes will be response rate (RR), disease control rate (DCR), progression-free survival (PFS) and overall survival (OS). Best response will be classified per RECIST criteria into complete response (CR), partial response (PR), stable disease (SD) and progressive disease (PD). Disease control will be the combination of CR + PR + SD. Kaplan-Meier survival curves will be used to estimate median PFS and OS. All statistical tests will be conducted using SAS version 9.2 (SAS Institute Inc).

Analysis of CGA results will be descriptive and will describe mean, median and standard deviations of scores at baseline and at follow up time points. CGA deficits will be captured at baseline and follow up time points. Each domain will be evaluated individually and scores will be compared between baseline and follow up time points. Overall CGA deficits will be examined and proportion of patients who decline in more than 1 domain will be determined for each time point.

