### **Determination of sample size**

Based on data from the CORRECT trial, an anticipated grade 3-4 toxicity rate of 40-50% is expected for our study. This is slightly lower than the observed grade 3-4 toxicity rate seen among patients > 65 years in the CORRECT trial. However, we hypothesize that starting at a lower dose and instituting extensive supportive care will lower the observed toxicity rate in our patient population. Using a sample size of 60 subjects with an expected toxicity rate of 45%, we will have a 90% CI of [0.341, 0.564] and an approximate 12% margin of error. Our plan is to accrue 3-4 patients per month among the four participating sites.

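### The synopsis claims about a 10-point margin at 95% confidence from 60 patients; the margin is 12 to 13 points, and Section 12 gives a different level and margin for the same sample size

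*Combined protocol and SAP*

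**What the plan says.** The precision of the toxicity rate is stated twice.

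- **Synopsis, plan for statistical analysis.** The planning rate is introduced with "Based on expected grade 3-4 toxicity rates of 40-50" (per cent), and the claim is that "a sample size of 60 patients will give approximately 10% margin of error with 95% confidence interval".
- **Section 12, Determination of sample size.** The same range is given ("an anticipated grade 3-4 toxicity rate of 40-50% is expected for our study"). The calculation begins "Using a sample size of 60 subjects with an expected toxicity rate of 45" (per cent) and concludes "we will have a 90% CI of [0.341, 0.564] and an approximate 12% margin of error".

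Neither place names an interval method.

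Section 12, Statistical and analytical plans, defines the outcome: "The primary end-point is grade 3-5 toxicity incidence rates". The analysis it then describes is "Descriptive statistics (counts and percentages) for grade 3 and 4 toxicity rates". It mentions no confidence interval for the primary rate, and no null rate, test or decision rule.

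**The concern.** For a fixed sample size, rate and interval method, raising the confidence level widens the interval. The plan has it the other way round: 10 points at 95% in the synopsis, 12 points at 90% in Section 12. The two statements cannot both be right, whichever method was used.

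With no hypothesis test on the primary endpoint, the width of the interval is the only statistical reason given for enrolling 60 patients. If the stated width is wrong, so is the justification. The choice of level would also carry into the report. The synopsis names a historical control, and the clinical experience section quotes a grade 3 or higher rate of 57% for patients aged 65-74 in the earlier phase III trial. If 27 of 60 patients (45%) had the event, every 95% interval tabulated below has its upper limit above 57% (0.575 to 0.584), and every 90% interval has it below (0.556 to 0.564). The same data would read differently against that benchmark, and the analysis section does not say which level applies.

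**Working it through.** **Inputs.** n = 60 (synopsis and Section 12); rate 40-50% (both); planning rate 45%, that is 27/60 (Section 12); stated margins 10 points at 95% (synopsis) and 12 points at 90% (Section 12).

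**Step 1: reproduce Section 12's interval.** The documents name no method, so several were tried at 27/60 and 90%. The Wilson interval with continuity correction matches to three decimals. With z = 1.645, z² = 2.7055 and p = 0.45:

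- Lower limit: [2np + z² − 1 − z√(z² − 2 − 1/n + 4p(n(1−p) + 1))] / [2(n + z²)] = (55.706 − 12.940) / 125.411 = 0.3410
- Upper limit: [2np + z² + 1 + z√(z² + 2 − 1/n + 4p(n(1−p) − 1))] / [2(n + z²)] = (57.706 + 12.982) / 125.411 = 0.5636

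The other 90% intervals do not match at both ends: Wald 0.3444-0.5556, Wald with continuity correction 0.3360-0.5640, Wilson 0.3488-0.5555, Jeffreys 0.3477-0.5558, exact 0.3398-0.5640.

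The half-width of the printed interval is (0.564 − 0.341)/2 = 0.1115. Its arms from 0.45 are 10.9 and 11.4 points. The nearest whole number is 11, not 12.

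**Step 2: test the synopsis margin.** The Wald half-width is z√(p(1−p)/n). At 95% (z = 1.960):

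- p = 0.40: 1.960 × √(0.24/60) = 1.960 × 0.06325 = 0.1240
- p = 0.45: 1.960 × √(0.2475/60) = 1.960 × 0.06423 = 0.1259
- p = 0.50: 1.960 × √(0.25/60) = 1.960 × 0.06455 = 0.1265

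Half-widths in percentage points by method:

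| Method | 95%: 24/60 | 95%: 27/60 | 95%: 30/60 | 90%: 24/60 | 90%: 27/60 | 90%: 30/60 |
|---|---|---|---|---|---|---|
| Wilson | 12.03 | 12.21 | 12.26 | 10.19 | 10.34 | 10.39 |
| Jeffreys | 12.16 | 12.34 | 12.40 | 10.25 | 10.40 | 10.46 |
| Wald | 12.40 | 12.59 | 12.65 | 10.40 | 10.56 | 10.62 |
| Wilson, continuity-corrected | 12.81 | 12.99 | 13.05 | 10.98 | 11.13 | 11.18 |
| Exact (Clopper-Pearson) | 12.95 | 13.13 | 13.19 | 11.05 | 11.21 | 11.26 |
| Wald, continuity-corrected | 13.23 | 13.42 | 13.48 | 11.24 | 11.40 | 11.45 |

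The smallest 95% value is 12.03. For every method, the smallest 95% half-width in the 40-50% range exceeds the largest 90% half-width, so no rate in that range reconciles the two statements.

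**Step 3: what 10 points would mean.** At n = 60, the Wald confidence level for a 10-point margin is 2Φ(0.10/√(p(1−p)/n)) − 1 = 88.6%, 88.1% and 87.9% at 40%, 45% and 50%. The sample size for a 10-point Wald margin at 95% is 1.960² × p(1−p)/0.10², rounded up: 93, 96 and 97.

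**Step 4: Section 12's apparent method at the synopsis's level.** The continuity-corrected Wilson 95% interval at 27/60 is 0.3233-0.5831, a half-width of 12.99 points. The exact 95% interval is 0.3212-0.5839, a half-width of 13.13 points.

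**The case against.** The best defence is that the synopsis has only the wrong label. At two-sided 90%, the level Section 12 uses, the Wald half-width is 10.4-10.6 points and the Wilson 10.2-10.4, which fits a claim of about 10. That may well be how the figure arose, but the text says 95%, and the reader has to take it at its word.

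Secondly, Section 12 is the dedicated sample size section. It prints the interval limits beside the margin, so calling 11.15 points about 12 errs on the cautious side and misleads little. This stands in part: on its own it would be a rounding remark. It matters here because correcting the synopsis to Section 12's 12% would carry over a margin that does not match its level.

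Thirdly, nothing operational depends on the margin. The accrual hold and the safety review triggers in Section 11 use counts of treatment delays and serious events, and any reported interval will come from the observed data. That limits the harm, but it does not make the stated justification correct.

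Lastly, the 40-50% expectation is given for grade 3-4, so moving the precision statement to grade 3-5 could attach that rate to another endpoint. The caution is fair. A statement conditional on an observed count avoids the problem, because the interval depends only on that count and n.

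**Conclusion.** The concern holds. The synopsis margin is wrong at its stated level: the 95% half-width at n = 60 and 40-50% is 12.0-13.2 points by Wilson, Wald or exact methods (up to 13.5 with the continuity-corrected Wald), so precision is overstated by about 2 to 3 points. The synopsis and Section 12 also contradict each other on both level and margin, and nothing elsewhere in the plan settles which was intended. Section 12's interval is valid; only its 12% label is off, by about 1 point.

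The conclusion assumes a two-sided interval for a single proportion with all 60 patients evaluable. It does not depend on the choice of method. That Section 12 used a continuity-corrected Wilson interval is inferred from the match and is for the sponsor to confirm. The error does not invalidate the design or call for a larger trial, but the figure that justifies the sample size should be correct.

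**What to change.** Keep 60 patients. In both the synopsis and Section 12, Determination of sample size, give one confidence level, one named method and the matching margin. Either:

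- **(a) 95%:** *If 27 of 60 patients (45%) have a grade 3-5 toxicity, the exact (Clopper-Pearson) 95% confidence interval is 0.32 to 0.58, a margin of about 13 percentage points.*
- **(b) 90%:** *If 27 of 60 patients (45%) have a grade 3-5 toxicity, the 90% confidence interval (Wilson with continuity correction) is 0.341 to 0.564, a margin of about 11 percentage points.* The sponsor should confirm the method.

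In Section 12, Statistical and analytical plans, add a sentence that the primary grade 3-5 toxicity rate will be reported with that same interval. Both wordings use the primary endpoint's grade range and are conditional on a count. If the 40-50% expectation is kept beside them, say whether it refers to grade 3-4 or grade 3-5.

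The cost is wording in two places and one added sentence. The synopsis margin widens by about 3 points under (a) or 1 point under (b), and Section 12's stated 12% moves by about 1 point either way. No extra patients are needed.

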## List of abbreviations

ADL	Activities of Daily Living
ALT	Alanine aminotransferase
Ang	Angiopoietin
aPTT	Activated partial thromboplastin time
AST	Aspartate aminotransferase
BID	bis in die , twice daily
B-Raf	B isoform of Rapidly Accelerated Fibrosarcoma protein
BUN	Blood Urea Nitrogen
c-KIT	Stem Cell Factor Receptor Tyrosine Kinase
CR	Complete Response
C-RAF	C isoform of Rapidly Accelerated Fibrosarcoma protein
CTCAE	Common Terminology Criteria for Adverse Events
DCE	Dynamic Contrast Enhanced
ECOG	Eastern Cooperative Oncology Group
EGFR	Epidermal growth factor receptor
ERK	Extracellular Signal-regulated Kinases
FDA	Food and Drug Administration
FGFR	Fibroblast Growth Factor Receptor
FLT3	FMS-like Tyrosine Kinase 3
GCP	Good Clinical Practice
GMP	Good Manufacturing Practice
HCC	Hepatocellular Carcinoma
HFSR	Hand-foot-skin reaction
IB	Investigator's Brochure
IC 50	Half Maximal Inhibitory Concentration
ICF	Informed Consent Form
ICH	International Conference on Harmonisation
IR	Immediate Release
IRB	Institutional Review Board

MAPK	Mitogen Activated Protein Kinase
MEK	MAP Kinase / ERK Kinase 1
NM	Nano molar
NYHA	New York Heart Association
PD	Progressive Disease
PDGFR- $\beta$	Platelet Derived Growth Factor Receptor-beta
PFS	Progression free survival
PO	per oris , oral
PR	Partial Response
PS	Performance Status
PTT	Partial thromboplastin time
QD	quaque die , once daily
RAF	Rapidly Accelerated Fibrosarcoma
RAS	Rat sarcoma
RCC	Renal Cell Carcinoma
RECIST	Response Evaluation Criteria for Solid Tumors
RET	Rearranged during transfection
RTK	Receptor Tyrosine Kinase
SAE	Serious Adverse Event
SD	Stable Disease
SUSARs	Suspected Unexpected Serious Adverse Reactions
TIE2	Tyrosine kinase with Immunoglobulin and Epidermal Growth Factor (EGF) homology domain 2
TK	Tyrosine Kinase
TTP	Time to Progression
VEGF	Vascular Endothelial Growth Factor
VEGFR	Vascular Endothelial Growth Factor Receptor

## 1. Introduction

### Background

More than half of all patients diagnosed with colorectal cancer are above the age of 65. Yet, only about 20% of patients in this age group were enrolled in the clinical trials on which our treatment decisions are based. Furthermore, it is well-established that adverse events and diminished quality of life are more likely to accompany treatment in this age group. This lack of data leads to variations in treatment patterns among older adults making them less likely to receive standard therapies. It is therefore important to design trials specifically for older patients which incorporate tools to measure health status factors that can be used to identify patients most likely to benefit from treatment.

### Rationale of the study

Limited evidence exists to guide risks and benefits of the multi-kinase inhibitor, regorafenib, in the older adult. Participants in the Phase III CORRECT trial that led to approval of regorafenib in previously treated mCRC had a median age of 61. The small number of older patients (38 subjects  $\geq 75$  years of a total  $n=503$ ) in this study had a disproportionately higher risk of any  $\geq$  grade 3 toxicities (66% for  $\geq 75$  years vs. 52% for  $< 65$  years). More safety information is needed – especially since many older patients are not candidates for combination cytotoxic chemotherapy and may be candidates for the use of regorafenib earlier in the course of the disease than their younger counterparts.

The management of older colon cancer patients must be tailored to the patient's overall functional status, risk of toxicities and comorbidities. Advanced age alone should not preclude patients from receiving standard anti-cancer therapy and the patient's physiologic age should guide treatment decisions. Tools such as the Comprehensive Geriatric Assessment (CGA) which is incorporated in this study need to be developed to aid the oncologist and patient in the shared decision process of treatment planning.

A special focus of this study will be to provide intensive education and support for preventing and managing skin toxicity (hand-foot syndrome) along with other common toxicities. This will be done according to standard guidelines developed by the sponsor. It is known that the elderly are particularly vulnerable to toxicities and we feel it is important that close and regular monitoring is provided for all participants in the study. Our hope is that this study will serve as a model for use of regorafenib in the geriatric patient population.

This study is timely because the use of combination cytotoxic chemotherapy (FOLFOX or FOLFIRI) versus monotherapy remains an issue of active debate in the management of older patients with metastatic colon cancer. The FOCUS2 trial, the largest randomized clinical trial in older patients with metastatic colon cancer, was recently published. The study randomized older patients with untreated metastatic colon cancer to capecitabine/5-FU with or without oxaliplatin with an initial empiric 20% dose reduction. The addition of oxaliplatin resulted in improved response rates and a trend towards improvement in PFS but no improvement in OS. The rate of grade 3 or higher toxicity was not increased with the addition of oxaliplatin at this lower dose. For now, the benefit of combination chemotherapy for adults  $\geq 65$  years of age is questionable

and considered on an individual patient basis. Additional treatment options, such as regorafenib, would be helpful and need to be evaluated carefully in this patient population.

## Regorafenib

Regorafenib has potent preclinical antitumor activity and long-lasting anti-angiogenic activity as measured by dynamic contrast enhanced (DCE) – magnetic resonance imaging (MRI).

Regorafenib is a small molecule inhibitor of multiple membrane-bound and intracellular kinases involved in normal cellular functions and in pathologic processes such as oncogenesis, tumor angiogenesis, and maintenance of the tumor microenvironment. In *in vitro* biochemical or cellular assays, regorafenib or its major human active metabolites M-2 and M-5 inhibited the activity of RET, VEGFR1, VEGFR2, VEGFR3, KIT, PDGFR-alpha, PDGFR-beta, FGFR1, FGFR2, TIE2, DDR2, Trk2A, Eph2A, RAF-1, BRAF, BRAFV600E, SAPK2, PTK5, and Ab1 at concentrations of regorafenib that have been achieved clinically. In *in vivo* models, regorafenib demonstrated anti-angiogenic activity in a rat tumor model and inhibition of tumor growth as well as anti-metastatic activity in several mouse xenograft models including some for human colorectal carcinoma.

## Preclinical

In vivo, regorafenib exhibited anti-angiogenic and anti-proliferative effects in human colon and breast xenografts as demonstrated by a reduction in microvessel area, reduced Ki-67 staining, and reduced pERK1/2 staining in tissue sections from tumor xenografts, and dose-dependent inhibition of growth in multiple xenograft models (breast, colon, renal, NSCLC, melanoma, pancreatic, thyroid, ovarian). Immunohistochemical ex-vivo studies with a phospho-specific monoclonal anti-ERK 1 / 2 antibody demonstrated inhibition of the MAPK pathway five days after treatment with regorafenib in 2 of 3 tumor models examined (MDA-MB 231 and BxPC-3), but not in NSCLC (H460).

In addition, all tested human tumor xenografts (MDA-MB-231, H460, BxPC-3 and Colo-205) demonstrated a significant reduction in new blood vessels by histomorphometry as detected in tumor samples using a murine CD31 antibody. These data suggest that regorafenib can target the tumor cell MAPK pathway (tumor cell survival) and tumor vasculature in some but not all tumors.

## Clinical Experience

Two phase III global randomized studies have evaluated the efficacy of regorafenib. The CORRECT (Patients with metastatic colorectal cancer treated with regorafenib or placebo after failure of standard therapy) trial is an international, multicenter, randomized, double-blind, placebo-controlled study that enrolled 760 patients with mCRC whose disease had progressed after approved standard therapies. Metastatic colorectal cancer patients were randomized to regorafenib plus best supportive care (BSC) or placebo plus BSC. Treatment cycles consisted of 160 mg of regorafenib (or matching placebo) once daily for three weeks on / one week off plus BSC. The primary endpoint of this trial was overall survival. Secondary endpoints included

progression-free survival, objective tumor response rate and disease control rate. The safety and tolerability of the two treatment groups were also compared.

At a preplanned second interim analysis, there was a statistically significant survival benefit for regorafenib. The estimated hazard ratio for overall survival was 0.773 (95% confidence interval [CI], 0.635 to 0.941; 1-sided  $p = .0051$ ). Patients treated with regorafenib had a median overall survival of 6.4 months, compared with 5.0 months for placebo — a 29% increase in survival. In addition to improved overall survival, progression-free survival was superior; median progression-free survival was 1.9 months (95% CI, 1.88 to 2.17) for regorafenib and 1.7 months (95% CI, 1.68 to 1.74) for placebo. The estimated hazard ratio for progression-free survival was 0.493 (95% CI, 0.418 to 0.581; 1-sided  $p < .000001$ ). There was a substantial difference in disease control rate in the regorafenib and placebo groups (44% vs. 15%;  $p < .000001$ ).

Regorafenib demonstrated comparable efficacy benefits across patient subgroups analyzed including age, number of mets, number of lines of prior therapy, and kras status.

The most frequent grade 3+ adverse events in the regorafenib (versus placebo) group were hand-foot skin reaction (17%), fatigue (15%), diarrhea (8%), hyperbilirubinemia (8%), and hypertension (7%). The efficacy and safety results from the CORRECT study supported FDA approval in September 2012.

The regorafenib treatment arm in the CORRECT study included 309 patients < 65 years (307 evaluable for safety), 155 patients 65-74 years and 38 patients  $\geq 75$  years. The OS hazard ratio was 0.72 (95% CI 0.56-0.91) in patients <65 years and 0.86 (95% CI 0.61-1.19) in patients  $\geq 65$  years. The rate of grade  $\geq 3$  adverse events was 52% for patients <65 years, 57% for patients 65-74 years and 66% for patients  $\geq 75$  years. Dose modification was necessary for 76% of patients < 65 years, 73% for patients 65-74 years and 84% for patients  $\geq 75$  years. This underscores the importance of close monitoring and good supportive care for older patients on regorafenib.

## Comprehensive Geriatric Assessment

All participants will undergo an abbreviated cancer-specific comprehensive geriatric assessment (CGA) at baseline, at 4 weeks, and then every 3 months while on study (+/- 7 days). Common assessment instruments in oncology (e.g. Karnofsky performance status) do not address critical geriatric domains that predict morbidity and mortality in the older patient (e.g., functional status, comorbidity and social support). A prospective study of 500 older adults with cancer demonstrated that traditional oncology functional assessment tools could not identify older adults at risk for chemotherapy toxicity. However, a predictive model that includes geriatric assessment questions could identify such individuals.

This validated cancer-specific CGA includes a compilation of reliable and validated tools to assess geriatric domains such as comorbidity, functional status, physical performance, cognitive ability, psychological state, nutrition, medication review and social support. The CGA can detect unsuspected conditions that may affect cancer treatment in more than 50% of older patients. Repetto et al. demonstrated that CGA added information to standard oncology performance measures such as Karnofsky performance score which is a one-item measure of function that was validated in younger patients. CGA has great potential to identify areas of

vulnerability and interventions that could help improve outcomes (e.g. reducing therapy-related toxicity) in older cancer patients. The initial study of this tool illustrated feasibility as demonstrated by a short mean time to completion of 27 minutes. Furthermore, 90% of patients were satisfied with the questionnaire length, and 78% were able to complete the self-administered portion on their own.

The abbreviated cancer-specific CGA was also found to be feasible for use by the Cancer and Aging Leukemia Group-B (CALGB 360401). Previous clinical studies, including the FOCUS2 trial, have demonstrated that factors within a CGA can better assess toxicities and aid with management decision. Based on these data, therefore, our study will incorporate CGA to assess the relative safety profile of regorafenib in the elderly population. The specific instruments used in our study have been slightly modified from the CGA data published by Hurria et al but address identical geriatric domains of interest. This CGA format is currently used in the SOCARE (Specialized Oncology Care and Research in the Elderly) multi-disciplinary clinic based at the University of Rochester Medical Center that is run by [name]. Staff at all sub-sites will be trained to conduct the CGA in a similar and replicable manner. This training will be overseen by [name] and her experienced staff.

COMPREHENSIVE GERIATRIC ASSESSMENT

DOMAIN	TOOL	SCORE SIGNIFYING IMPAIRMENT
Background Information	➤ Demographics: ➤ Education ➤ Marital status ➤ Living Arrangements ➤ Health status ➤ Employment status ➤ Driving status ➤ Age ➤ Zip code ➤ Gender ➤ Ethnicity ➤ Race ➤ Insurance/health care ➤ Income ➤ Social Services	
Physical function	➤ ADL ➤ IADL ➤ Fall history	➤ Any ADL or IADL impairment ➤ Any history of fall
Objective physical performance	➤ SPPB	➤ ≤ 9
Comorbidity	➤ Average number of comorbid conditions	➤ >5
Nutrition	➤ BMI ➤ MNA	➤ <21 ➤ ≤ 11
Social support	➤ OARS Medical Social Support	➤ Any deficit noted
Polypharmacy	➤ Number of total medications	➤ ≥5 medications
Psychological	➤ GDS	➤ ≥ 5
Cognition	➤ BOMC ➤ Mini Cog	➤ >10 ➤ abnormal
Screening	➤ VES-13	➤ ≥3
Quality of Life	➤ FACT-C ➤ FACT-F ➤ MDASI	

ADL: Activity of daily living  
MNA: Mini nutritional assessment  
SPPB: Short physical performance battery  
BMI: Body mass index  
VES: Vulnerable elderly survey  
MDASI: MD Anderson Symptom Inventory

GDS: Geriatric Depression scale  
IADL: Instrumental activity of daily living  
BOMC: Blessed orientation-memory-concentration  
FACT-C: Functional Assessment of Cancer Therapy-Colon  
FACT-F: Functional Assessment of Cancer Therapy-Fatigue

